5.1.5 Monitoring of dose administration

Patients will be monitored during and after the infusion with assessment of vital signs at the times specified in the Study Protocol.

In the event of a ≤Grade 2 infusion-related reaction, the infusion rate of study drug may be decreased by 50% or interrupted until resolution of the event and re-initiated at 50% of the initial rate until completion of the infusion. For patients with a ≤Grade 2 infusion-related reaction, subsequent infusions may be administered at 50% of the initial rate. Acetaminophen and/or an antihistamine (eg, diphenhydramine) or equivalent medications per institutional standard may be administered at the discretion of the investigator. If the infusion-related reaction is ≥Grade 3 or higher in severity, study drug will be discontinued.

As with any antibody, allergic reactions to dose administration are possible. Appropriate drugs and medical equipment to treat acute anaphylactic reactions must be immediately available, and

Drug Substance Azacitidine/Decitabine (ASTX727)

Study Code 15-11430

Edition Number 13.0

Date 09202024

study personnel must be trained to recognize and treat anaphylaxis. The study site must have immediate access to emergency resuscitation teams and equipment in addition to the ability to admit patients to an intensive care unit if necessary

5.1.6 Accountability and dispensation

Clinical supplies must be stored in a secure, limited-access location under the storage conditions specified on the label. Receipt and dispensing of trial medication must be recorded by an authorized person at the trial site.

5.1.7 Disposition of unused investigational study drug

The investigator is responsible for keeping accurate records of the clinical supplies received from Astrazeneca/MedImmune and ASTX Pharmaceuticals, the amount dispensed to and returned by the subjects and the amount remaining at the conclusion of the trial.

Upon completion or termination of the study, all unused and/or partially used investigational product will be destroyed at the site per institutional policy. It is the Investigator's responsibility to arrange for disposal of all empty containers, provided that procedures for proper disposal have been established according to applicable federal, state, local and institutional guidelines and procedures, and provided that appropriate records of disposal are kept. Certificates of delivery and destruction must be signed.

5.2 Azacitidine/Oral Decitabine (ASTX727)

Azacitidine, Vidaza®, has the following chemical structure:

Figure 2a. Chemical Structure of Azacitidine

Azacitidine is (4-amino-1- β -D-ribofuranosyl-s-triazin-2(1*H*)-one). The empirical formula is $C_8H_{12}N_4O_5$. The molecular weight is 244 amu.

Drug Substance Azacitidine/Decitabine (ASTX727)

Study Code 15-11430

Edition Number 13.0

Date 09202024

ASTX727 is under development as an FDC tablet for oral administration of cedazuridine (E7727) (100 mg), a novel cytidine deaminase inhibitor (CDAi), and decitabine (35 mg), an FDA-approved HMA for IV infusion (Figure 2b and Figure 2c). The CDAi cedazuridine enables the oral bioavailability of decitabine.

Figure 2b. Molecular Structure of Cedazuridine

Figure 2c. Molecular Structure of Decitabine

Nomenclature and properties of the components of ASTX727 (cedazuridine and decitabine) are provided in Table 4.

Table 4: Nomenclature and Properties: Cedazuridine and Decitabine

	Cedazuridine	Decitabine
Compendial Name	cedazuridine	decitabine
Chemical Name (IUPAC)	(4R)-1-[$(2R,4R,5R)$ -3,3-difluoro-4-hydroxy-5- (hydroxymethyl)oxolan-2-yl]-4-	4-amino-1-[(2 R ,4 S ,5 R)-4-hydroxy-5-(hydroxymethyl)oxolan-2-yl]-1,3,5-triazin-2(1 H)-one
	hydroxy-1,3-diazinan-2-one	
(CAS) Registry Number	1141397-80-9	2353-33-5
Chemical Formula	C9H14F2N2O5	C8H12N4O4
Molecular Weight	268.21 Daltons	228.21 Daltons

Drug Substance Azacitidine/Decitabine (ASTX727)

Study Code 15-11430 Edition Number 13.0

Date 09202024

Pharmacologic Class Cytidine deaminase inhibitor Anatomical therapeutic chemical

(ATC) code L01BC08, Antineoplastic and

immunomodulating agents, pyrimidine analogues.
Decitabine is a cytosine deoxynucleoside analogue that inhibits DNA methyltransferase.a Slightly soluble in ethanol/water

(50/50), methanol/water (50/50)

and methanol, sparingly soluble in water and soluble in

dimethylsulfoxide (DMSO).

Solubility Soluble in dimethylsulfoxide and

0.1 M HCl, sparingly soluble in water and pH 7.2 buffer, slightly soluble in methanol and ethanol, and insoluble in n-heptane, ethyl acetate, acetonitrile, 1-octanol, and methyl test buttle other. Not

methyl tert-butyl ether. Not

hygroscopic.

a Source: Decitabine European Public Assessment Report (EPAR) accessed 09 April 2019. https://www.ema.europa.eu/en/documents/product-information/dacogen-epar-product-information en.pdf

5.2.1 Formulation/packaging/preparation/storage

Azacitidine (Vidaza®) is supplied as a lyophilized powder in 100 mg single-use vial, and should be reconstituted aseptically with 4 mL sterile water for injection. The diluent should be injected slowly into the vial. Vigorously shake or roll the vial until a uniform suspension is achieved. The suspension will be cloudy. The resulting suspension will contain azacitidine 25 mg/mL.

Preparation for Immediate Administration:

Azacitidine doses should be drawn up into 1 to 4 syringes of equal volume per institutional guidelines. The product must be administered within 1 hour after reconstitution when stored at room temperature.

Preparation for Delayed Administration:

The reconstituted product may be kept in the vial or drawn into a syringe. The product must be refrigerated immediately, and may be held under refrigerated conditions (2°C - 8°C, 36°F- 46°F) for up to 8 hours. After removal from refrigerated conditions, the suspension may be allowed to equilibrate to room temperature for up to 30 minutes prior to administration.

Reconstituted azacitidine may be stored for up to 1 hour at 25°C (77°F) or for up to 8 hours between 2 and 8°C (36 and 46°F). The azacitidine vial is single-use and does not contain any preservatives. Unused portions of each vial should be discarded properly. Do not save any unused portions for later administration.

Azacitidine is a cytotoxic drug and, as with other potentially toxic compounds, caution should be exercised when handling. Several guidelines on this subject have been published (ASHP,

Clinical Study Protocol

Drug Substance Azacitidine/Decitabine (ASTX727)

Study Code 15-11430

Edition Number 13.0

Date 09202024

2006; NIH, 1999; NIOSH, 2004; OSHA, 1999; Polovich, 2005). If reconstituted azacitidine comes into contact with the skin, immediately and thoroughly wash with soap and water. If it comes into contact with mucous membranes, flush thoroughly with water. Procedures for proper handling and disposal of azacitidine should be applied according to standards established at each facility for cytotoxic drugs.

Prior to development of ASTX727 tablet (see below), cedazuridine and decitabine were administered separately in capsules.

The new ASTX727 tablet is a fixed-dose combination of 100 mg cedazuridine and 35 mg decitabine for oral administration. The drug product is a red, oval shaped film-coated, immediate-release tablet (Figure 3). The formulation excipients include lactose, hypromellose, croscarmellose sodium, colloidal silicon dioxide, magnesium stearate, and Opadry II 85F15458 Red. The Opadry is a tablet coating formula that contains titanium dioxide, polyvinyl alcohol, polyethylene glycol, tale, and iron oxide red. The clinical drug products are either plain faced on both sides, or have a debossed marking of "H35" on one side and plain faced on the other. This tablet was used in the Phase 3 trial.

Figure 3. ASTX727 Tablet

All drug products are packed in 5-count opaque high-density polyethylene (HDPE) bottle with a child resistant closure. Each bottle contains either 1 or 2 desiccant canisters for moisture absorption. The desiccant canisters should remain in the bottle at all times and must not be ingested. Tablets are to be stored on site as indicated in the study-specific Pharmacy Manual (provided by Astex). Tablets should be dispensed by the study pharmacist according to institutional policy and per study protocol, and at-home storage instructions should be given to the study subject.

5.2.2 Doses and treatment regimens

All subjects will be administered either a fixed dose and schedule of durvalumab (MEDI4736) and tremelimumab with azacitidine or a fixed dose and schedule of durvalumab (MEDI4736) with ASTZ727 The dose and schedule of azacitidine or decitabine will determined by the dose escalation schema (Sections 3.2 and 6.2, Table 2). For those patients receiving azacitidine, in Cycle 2, azacitidine will be administered 60 minutes following the infusion of durvalumab. For subsequent cycles, azacitidine will be administered after the completion of the durvalumab infusion.

5.2.3 Dose administration

Subjects who enter screening will be assigned the next available subject number. All eligible subjects will receive oral decitabine (ASTX727) at the assigned dose. Subjects will complete a self administration drug diary (**Appendix 8**). The dose will be taken at the same time (+/-1 hour) for the first 5 days of each cycle. If the subject misses the dose and remembers before 6:00 PM that day, the subject may make-up the dose. If it is after 6:00 PM, the subject should wait until the next scheduled dosing time (the next day) and take the next scheduled dose. If the dose is vomited, the patient should not re-dose. The tablets cannot be crushed, chewed, or dissolved in water. The drug should be taken with 8 fluid ounces of water. The drug should be taken in the fasted state (no food for at least 2 hours before and 2 hours after taking the dose). The bottles containing the tablets should be stored at room temperature.

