3. STUDY DESIGN

3.1 Overview of study design

This is a non-randomized, open-label, Phase Ib study to assess the safety and efficacy of oral decitabine (ASTX727) and durvalumab (MEDI4736) combination therapy in the treatment of patients with recurrent and/or metastatic squamous cell carcinoma of the head and neck (SCCHN) who have progressed during or after treatment with anti-PD-1, anti-PD-L1, and/or anti-CTLA-4 for recurrent and/or metastatic disease. The primary endpoint is to determine the BED of oral decitabine (ASTX727) in combination with durvalumab (MEDI4736) therapy. The secondary endpoint is to assess the safety of oral decitabine (ASTX727) in combination with durvalumab (MEDI4736) therapy.

The trial opened with the use of subcutaneous (SC) injection of azacitidine. All patients received azacitidine SC injection on either Days 1-5 alone or Days 1-5 and 8-12 in a 4-week cycle, durvalumab (MEDI4736) 1500 mg via intravenous (IV) infusion every 4 weeks (q4w), and tremelimumab 75 mg via IV infusion q4w. Azacitidine was administered alone in Cycle 1 and the combination of azacitidine, durvalumab, and tremelimumab therapy was started in Cycle 2. Dose Limiting Toxicity (DLT) was assessed through 28 days post Cycle 2. After cycle 2, patients continued with azacitidine, durvalumab and tremelimumab combination therapy for Cycles 3-5 and azacitidine and durvalumab for Cycles 6-12 or until confirmed PD, initiation of alternative cancer therapy, unacceptable toxicity, withdrawal of consent, or another discontinuation criterion is met, whichever occured first. However, treatment consisting of 5 to 10 daily visits for a large-volume SC injection continuing for several months or even years, represented a significant hardship for patients with possible consequences of non-compliance or earlier discontinuation of a beneficial treatment. Therefore, an oral DNA methyltransferase inhibitor is being evaluated to ease the burden of daily visits for those patients who are benefitting the most and need continuing treatment for long periods. Furthermore, since the oral DNA methyltransferase inhibitor is investigational, we plan to combine it with the FDA approved durvalumab.

Therefore, all patients enrolled with or after protocol version 11.0 will receive an oral tablet of ASTX727 (35 mg decitabine/100 mg cedazuridine) daily on either Days 1-3, Days 1-4, or Days 1-5 and durvalumab (MEDI4736) 1500 mg via IV infusion x 1 in a 4-week cycle. Oral

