3.2 Study schema

Figure 1. Study Flow Chart

Patients with recurrent or metastatic SCCHN who have progressed after to atment with an immunotherapy for recurrent or metastatic disease Durvalumab +/- tremelimumab +
dose escalation of DNA
methyltrasnferas inhibitor
(refer to charts below)

Progression Free Survival Objective Response Rate Overall Survival Biomarkers

Cohort (# of pts)	Azacitidine (28-day cycle)	Grade 3 or higher	2-fold DNMT1 inhibition in ≥50% of patients
D-1 (6)	20 mg/m2 on Days 1-5	MTD ²	BED ³
1 (6)	40 mg/m2 on Days 1-5	MTD ²	BED ³

Drug Substance Azacitidine/Decitabine (ASTX727)

Study Code 15-11430

Edition Number 13.0

Date 09202024

2 (6)	40 mg/m2 on Days 1-5 and 8-12	MTD ²	BED ³
3 (6)	75 mg/m2 on Days 1-5	MTD ²	BED ³

¹Azacitidine will be given starting Cycle 1 and durvalumab and tremelimumab will be given starting Cycle 2

³BED (biologically effective dose)

Cohort (# of pts)	Oral Decitabine (ASTX727) (28-day cycle)	Grade 3 or higher	10% decrease in LINE-1 methylation in ≥50% of patients
BD-1 (6)	ASTX727 one tablet on Days 1-2	MTD ²	BED ³
B1 (6)	ASTX727 one tablet on Days 1-3	MTD ²	BED ³
B2 (6)	ASTX727 one tablet on Days 1-4	MTD ²	BED ³
B3 (6)	ASTX727 one tablet on Days 1-5	MTD ²	BED ³

¹Oral decitabine (ASTX727) will be given starting Cycle 1 and durvalumab will be given starting Cycle 2

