
Drug Substance Azacitidine/Decitabine (ASTX727)

Study Code 15-11430

Edition Number 13.0

Date 09202024

Although assessment of the BED is primary, the dose also needs to be safe. Each dose will be assessed for safety according to a stopping rule and a DLT toxicity definition as outlined in the protocol and statistical section. Decisions will then be made about dose escalations of oral decatibine (ASTX727). Subjects will be sequentially assigned to the cohorts. The first 6 enrolled subjects will ingest one tablet daily on Days 1-3 of a 28-day cycle. If two or more of the first six subjects experience a DLT, then the dose will be reduced and an additional six patients will be treated at the reduced dose. If two or more of the six at the reduced dose experience a DLT, then the study will be terminated. If at any time during accrual to a cohort, 2 or more patients in a cohort experience DLT, enrollment to that cohort will be terminated. If less than two of the six patients treated at dose level 1 experience a DLT, a subsequent group of six patients will receive dose level 2.

Patients cannot change groups or dose assignments upon the initiation of the study protocol. Please refer to **Sections 5.1.2, 5.1.3, and 5.2.4**. for the administration and monitoring of administration of durvalumab (MEDI4736) and tremelimumab. Please refer to **Section 5.3** for the administration and monitoring of administration of oral decitabine (ASTX727).

Table 5a: Cohort size and dose escalation for oral decitabine (ASTX727)

Cohort (# of pts)	Oral decitabine (ASTX727) (28 day cycle)	Grade 3 or higher	2-fold DNMT1 inhibition in ≥50% of patients
BD-1 (6)	ASTX 727 one tablet daily on Days 1-2	MTD ¹	BED ²
B1 (6)	ASTX 727 one tablet daily on Days 1-3	MTD ¹	BED ²
B2 (6)	ASTX 727 one tablet daily on Days 1-4	MTD ¹	BED ²
B3 (6)	ASTX 727 one tablet daily on Days 1-5	MTD ¹	BED ²

 $^{^{1}}$ MTD (maximally tolerated dose) will be defined as that dose of azacitidine that results in \leq 2 of 6 patients experiencing a DLT

Table 5b: Cohort size and dose escalation for azacitidine

²BED (biologically effective dose) will be defined as that dose of oral decitabine (ASTX727) that results in at least a 10% decrease in LINE-1 methylation in pre- and on-treatment biopsy samples in >50% of treated subjects

Drug Substance Azacitidine/Decitabine (ASTX727)

Study Code 15-11430

Edition Number 13.0

Date 09202024

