6.3 Dose Escalation Decision Rules

Dose escalation monitoring

In order to ensure that patients are receiving the assigned dose of drug, oral decitabine (ASTX727), several measures will be employed.

Printed orders will be available.

The principal investigator, research nurse, and data manager will review the available toxicity data prior to continuing to escalate the dose and enrolling patients into the new cohort.

Prior to the start of each new dose level (i.e. accrual of a new cohort), a dated letter will be sent to the pharmacy which describes the change in dose.

Stopping rules

Dose escalations will continue until one of the following stopping rules has been satisfied:

- 1. The BED has been determined.
- 2.If at any time during accrual to a cohort, 2 or more patients in a dose cohort experience DLT, enrollment to that dose cohort will be terminated and dose escalation will stop.
- 3. Two of six patients treated at a reduced dose of oral decitabine (ASTX727) on Days 1-2 of a 28 day cycle experience a DLT

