8.1.2 Treatment Phase

Procedures to be conducted during the treatment phase of the study are presented in the Schedule of Assessments. Screening procedures performed within 72 hours of Cycle 1 Day 1 (C1D1) of protocol treatment do not need to be repeated on C1D1. The treatment to be used in this trial is outlined below in **Table 6**.

- Complete physical exam
- Vitals signs and weight
- 12-lead ECG (in triplicate [2-5 minutes apart]), as clinically indicated
- ECOG Performance Status
- Adverse event/serious adverse event assessment
- Review of prior/concomitant medications
- Clinical laboratory tests for:
 - o Hematology (see Table 7)
 - o Clinical chemistry (see Table 8)
 - o TSH
 - o Coagulation (PT, PTT, INR), as clinically indicated
 - o Creatinine Clearance
 - o Serum pregnancy test (for women of childbearing potential only)
 - o Urinalysis (see Table 9)

Drug Substance Azacitidine/Decitabine (ASTX727)

Study Code 15-11430

Edition Number 13.0

Date 09202024

- Pharmacokinetic assessment
- Imaging by CT/MRI
- Bone scan, if baseline bone scan demonstrates metastatic disease
- Tumor biopsy sample for research analysis
- Peripheral blood draw for research analysis

Table 9 Trial Treatment

Drug	Dose/Potency	Dose Frequency	Route of Administration	Regimen/Treatment Period	Use
Durvalumab (MEDI4736)	1500 mg	Q4W	IV infusion	Day 1 of each 4 week cycle for 12 cycles ^a	Experimental
Tremelimumab	75 mg	Q4W	IV infusion	Day 1 of each 4 week cycle for 4 cycles ^a	Experimental
Tremelimumab	300 mg	Once	IV infusion	Day 1 of Cycle 2	Experimental
Azacitidine	40 mg/m2 or 75 mg/m2	QD	SC	Days 1-5 or Days 1-5 and 8-12 of each 4 week cycle for 12 cycles ^a	Experimental
Decitabine (ASTX727)	35 mg decitabine	QD	PO	Days 1-3, 1-4, or 1-5 of each 4-week cycle for 12 cycles ^a	Experimental

^aAzacitidine or decitabine will be administered alone in Cycle 1. For those patients receiving azacitidine, the combination of azacitidine, durvalumab, and tremelimumab therapy will start in Cycle 2. Patients will continue with azacitidine, durvalumab and tremelimumab combination therapy for Cycles 3-5 and azacitidine and durvalumab for Cycles 6-12. For those patients receiving decatibine, the combination of decatibine and durvalumab therapy will be given in Cycles 2-12.

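### Section 5.2.3 tells every ASTX727 subject to dose for five days per cycle, which is right only for dose level B3

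*Combined protocol and SAP*

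**What the plan says.** Section 5.2.3 covers how subjects take ASTX727 at home: time of day, missed and vomited doses, fasting and the diary. It first says "All eligible subjects will receive oral decitabine (ASTX727) at the assigned dose". It then gives a day count for everyone: "The dose will be taken at the same time (+/-1 hour) for the first 5 days of each cycle".

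The other sections set the days by dose level.

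- Section 3.1: one tablet "daily on either Days 1-3, Days 1-4, or Days 1-5".
- Section 3.2, schema: four levels, starting with BD-1, "ASTX727 one tablet on Days 1-2", and rising by one day per level to B3 on Days 1-5.
- Section 6.2, Table 5a: the same four levels; B1, for example, is "ASTX 727 one tablet daily on Days 1-3".
- Section 6.3: the third stopping rule concerns a "reduced dose of oral decitabine (ASTX727) on Days 1-2 of a 28 day cycle".
- Section 8.1.2, Table 9: "Days 1-3, 1-4, or 1-5 of each 4-week cycle for 12 cycles".

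Section 5.2.2, directly above, refers the reader to Sections 3.2 and 6.2 for dose and schedule.

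**The concern.** Every ASTX727 level uses the same tablet once a day, so the levels differ only in days per cycle. A sentence that fixes that number at five for all subjects contradicts the variable under study, and it does so in the section that governs self-administration.

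A B1 or B2 subject who followed the sentence would take the level 3 schedule. Under Sections 3.1 and 11, level 3 opens only after accrual has been suspended, LINE-1 results from the first two levels have been reviewed, no biologically effective dose (BED) has been found, and it is judged safe to go on. A BD-1 subject would be taking more than the level that had just produced two or more dose-limiting toxicities (DLTs) in six.

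If such an error went unnoticed, the subject's DLT status and week-8 LINE-1 result would be counted at a level the subject did not receive. With six subjects per level and a two-DLT stopping rule, one such subject could alter a decision.

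**Working it through.** The plan gives no milligram total per cycle to reproduce. The check compares the stated days and converts them to dose.

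Inputs:

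- Tablet content: 35 mg decitabine, one tablet per dosing day (Sections 3.1 and 6.2).
- Days per cycle by level: BD-1 2, B1 3, B2 4, B3 5 (Section 3.2 and Table 5a).
- Days per cycle in Section 5.2.3: 5, all subjects.

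Formulas: planned dose = 35 mg × days for the level; literal dose = 35 mg × 5 = 175 mg; relative excess = (literal − planned) / planned.

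| Level | Planned dose per cycle | Excess if 5.2.3 is followed | Relative excess |
|---|---|---|---|
| B1 | 35 × 3 = 105 mg | 175 − 105 = 70 mg | 70/105 = +67% |
| B2 | 35 × 4 = 140 mg | 175 − 140 = 35 mg | 35/140 = +25% |
| B3 | 35 × 5 = 175 mg | 0 mg | 0% |
| BD-1 (only if opened) | 35 × 2 = 70 mg | 175 − 70 = 105 mg | 105/70 = +150% |

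B1 is where the oral phase starts and B2 is the next planned level. BD-1 opens only if at least two of six subjects at B1 have a DLT, so its figure is conditional.

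The clause can also be wrong for a B3 subject. Section 6.5.2.1 allows one dose reduction from the original dose, and Table 6 makes that reduction one cohort level. A B3 subject reduced once should dose on Days 1-4, which again conflicts with five days.

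Section 5.2.1 says the tablets come in bottles of five. If one full bottle were dispensed per cycle, the surplus would be 5 − 3 = 2 tablets in B1, 5 − 4 = 1 in B2 and 5 − 2 = 3 in BD-1. That is an assumption: the text does not give the quantity dispensed.

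**The case against.** The strongest reply is that nobody working from the whole protocol would be misled. Section 5.2.2 assigns dose and schedule to the escalation schema. Section 5.2.3 itself says subjects take the assigned dose, and Section 6.3 uses the word dose for the day schedule. On this reading the five-day clause is a stray day count inside a time-of-day rule.

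There are also controls. The study pharmacist dispenses (5.2.1), the diary and bottles come back to the clinic (5.2.4), unused drug is returned (5.2.5), and printed orders are available. Before each new level "a dated letter will be sent to the pharmacy which describes the change in dose" (6.3). Any oral amount above the specified dose is reportable as an overdose within 24 hours (10.3.3.1). Days 1-5 with durvalumab is itself a planned level, Cycle 1 is decitabine alone, and Section 1.4.2.5 treats the toxicity of five-day decitabine as familiar.

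Most of this stands. The intended schedule is recoverable and misdosing is unlikely. Three things remain. Neither 5.2.2 nor the assigned-dose sentence limits the five-day clause. Dispensing and the overdose definition both refer back to what the protocol specifies, and on this point it gives two answers. And a planned level is not one that a B1 or B2 subject has been cleared to receive.

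A reader might infer more: that subjects are being overdosed, that the escalation has collapsed into a single schedule, or that DLT and LINE-1 data sit at the wrong levels. The documents do not support any of these. They report no dosing event. The contents of the diary and the pharmacy manual are not in the text reviewed, so no five-day instruction to subjects has been shown.

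**Conclusion.** Section 5.2.3 is wrong as written for B1, B2 and, if it opens, BD-1; it is right for B3 unless that subject's dose has been reduced. Followed literally, it would add 67% to the per-cycle decitabine dose in B1 and 25% in B2, and 150% in BD-1. These figures assume one 35 mg tablet per day and a subject who follows the sentence exactly. They measure the discrepancy in the text and do not estimate how often misdosing would happen.

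This is an internal inconsistency that should be fixed, because it concerns safety and the only escalated ASTX727 variable. It does not make the design ambiguous and does not touch the operating characteristics. The conclusion depends on nothing outside the supplied text. What subjects are actually told could not be checked.

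**What to change.** In Section 5.2.3, replace the five-day clause with: *on each scheduled dosing day of the subject's currently assigned dose level (Table 5a: Days 1-2, 1-3, 1-4 or 1-5), including any dose reduction under Section 6.5.2*. Wording tied only to the cohort at entry would not do. A B2 subject reduced for toxicity should take Days 1-3, but cohort-only wording would send that subject back to Days 1-4.

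Confirm that the Appendix 8 diary and the number of tablets dispensed from the five-count bottles match the subject's current level.

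The cost is one phrase and one check of the diary and dispensing quantity. Sample size, stopping rules and analysis stay as they are.

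The same amendment could tidy some stale references: Table 2 in Sections 5.2.2, 6.1.2 and 6.5.2.1, Table 1 in schedule footnote d, and Section 5.3 in Section 6.2. That is housekeeping and adds no weight to this point.
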